### **Single use of products (Day 1 and Day 3)**

On Day 1 and Day 3, subjects will use the product they are randomized to only once in the morning between 6:00 am to 9:00 am, and will abstain from the product or other nicotine/tobacco-containing items for the rest of the day, i.e., subjects in the THS 2.2 arm will use one Tobacco Stick, subjects in the CC arm will smoke one CC, and subjects in the NNS arm will administer one spray into each nostril (leading to an estimated total administered amount of 1 mg nicotine).

	Sequence 1	Sequence 2	Sequence 3	Sequence 4
Day 1	THS 2.2	CC	THS 2.2	NNS
Day 3	CC	THS 2.2	NNS	THS 2.2

#### **6.2.3 Day of Discharge/Time of Discharge**

On the Day of Discharge (Day 4), smoking will be only allowed after all laboratory procedures and the spirometry have been performed. All examinations of the Day of Discharge will be conducted on Day 4 prior to the time of Discharge.

#### **6.2.4 Safety Period**

During the safety follow-up period, subjects are free to smoke according to their usual smoking habits.

#### **6.2.5 Stopping Rules for Investigational Product**

For safety purposes, using the THS 2.2, smoking the CC, or use of the NNS should be temporarily stopped in the event of any signs suggesting nicotine overexposure, e.g., gastrointestinal disturbance (nausea, vomiting, diarrhoea, stomach or abdominal pain), cold sweats, headache, dizziness and breathing problems or any reasons at the discretion of the Investigator.

### **6.3 Method for Assigning Subjects to Study Arms**

Randomization to product exposure sequence will be done through an Interactive Telephone and Web Response System.

Each sex and each of the smoking level (ISO nicotine levels  $\leq 0.6$  mg and  $> 0.6$  to  $\leq 1$  mg) will have a quota applied to ensure they represent at least 40% of the total study population allocated within each of the following analysis groups:

- Group-1: composed of sequences 1 and 2.

Confidentiality Statement: Data and information contained in this document are considered to constitute trade secrets and confidential commercial information, and the legal protections provided to such trade secrets and confidential information are hereby claimed under the applicable provisions of applicable law. No part of this document may be publicly disclosed without the written consent of Philip Morris Products S.A.

- Group-2: composed of sequences 3 and 4.

In particular, the maximum number of subjects having the same sex or nicotine level value will be limited to 26 in Group-1 and 10 in Group-2.

The randomization of the planned sample size of 62 subjects will be ensured by applying quota to the number of subjects per each sequence (22 subjects for sequences in Group-1, and 9 subjects for sequences in Group-2).

Subjects will be randomly assigned to one of the four product exposure sequences by means of a permuted-block schema. Block size and other randomization details will be available in the randomization plan.

The randomization plan will be generated by an independent statistician and none of the sponsor staff, investigators or study subjects will have access to the randomization schema prior to randomization.

## 6.4 Blinding

This is an open-label study; therefore, the subjects and investigators will be unblinded to subject's sequence. However, there will be a limited degree of blinding in the data review and data analysis process. In particular, PMI and CRO personnel will be blinded to the randomized sequence as summarized in the following table:

Blinded Study Personnel	End of Blinding Period
PMI and CRO study statisticians	After the Statistical Analysis Plan (SAP) finalization or PMI blind database review (*) , whichever comes last.
PMI data manager	After the finalization of PMI blind database review. (*)
PMI safety and clinical scientist	After the finalization of PMI blind database review (*) . Can be actively un-blinded before that time point in case of the occurrence of any safety question, when appropriate.

(\*) As part of the PMI Quality Control (QC) activity, data listings will be reviewed by PMI before database lock, with no access to the randomization sequence information.

Any PMI and CRO personnel who are not listed in the above table will be unblinded by default.

## 6.5 Investigational and Reference Point Product Accountability and Compliance

### 6.5.1 Dispensing Investigational and Reference Point Products

From Day -1 until Day 4, the THS 2.2, NNS, and CC will be dispensed by the Investigators or dedicated study staff, as per study design. Each dispense of the product will be recorded in a log. The log should include subject number, date and start time of product use. The product will not be promoted for commercial distribution or test market.

### 6.5.2 Storage and Accountability

The THS 2.2, NNS, and CC will be stored in a secured site storage place with access limited to the authorized personnel only. Full accountability of the distributed products will be ensured by designated staff. Subjects will return each butt of any used Tobacco Stick or CC immediately after use to the site staff for accountability. They will also return the NNS after use to the site staff. This will be documented in appropriate log. At the end of the study, unused CCs given to the site staff at Admission on Day -1 will be given back to the subjects.

### 6.5.3 Investigational and Reference Point Product Retention

Unused Tobacco Sticks and NNS will be destroyed if possible, or returned to the Sponsor upon study completion. The Tobacco Heating Devices will be returned to the Sponsor.

### 6.5.4 Compliance to Investigational and Reference Point Products

Compliance for all arms will be ensured by strict distribution of the products (product by product) and collection of used Tobacco Sticks, the CC butts and the NNS after use will be documented in appropriate logs.

In addition, in subjects using NNS, the compliance will be chemically verified using exhaled CO breath. The cut-off point for the CO breath test value to distinguish tobacco use vs. no tobacco use will be 10 ppm ([Benowitz et al, 2002](#)).

Furthermore, the CO breath test will be considered as one of the measures of compliance during the wash-out days in all subjects.

## 6.6 Restrictions

### 6.6.1 Smoking Restrictions

On Day 1 and Day 3, to avoid nicotine cross contamination, smokers of THS 2.2 and CC will smoke in dedicated separate rooms: one room for THS 2.2 and one room for CC. Every subject must smoke alone with an interval between subjects allowing ventilation of the room. Subjects receiving NNS must not have access to these rooms.

In the morning prior admission, subjects will be instructed not to smoke. At admission, smoking is only allowed during the designated smoking times from 6:00 am to 11:00 PM as detailed in the study design. Subjects will not have free access to their NNS, CC or Tobacco Sticks, which will be dispensed by the site staff individually as described in [Section 6.5.1](#).

Smoking is not allowed during study procedures except during blood sampling for nicotine PK on Day 1 and Day 3. Furthermore, smoking is not allowed on Day 4 until all laboratory tests and the spirometry have been conducted.

During the days of wash-out or single product use (for CC and THS 2.2 arms), no NNS or other products supportive to smoking abstinence must be used or will be provided to the subjects.

### 6.6.2 Dietary Restrictions

A standard diet will be designed by a dietitian for the whole confinement period. For each meal, the caloric and fat content should be controlled in order to avoid a “high-fat” diet. The FDA guidance on food-effect studies for bioequivalency testing identifies a “high-fat” diet as a diet which contains “approximately 50 percent of total caloric content of the meal [from fat] and is high in calories (approximately 800 to 1000 calories) ([FDA, 2002](#)).

Subjects are not allowed to bring their own food or beverages to the investigational site. Meals will be served according to the schedules provided in [Sections 9.2, 9.3.1, 9.3.2](#) and [9.4](#). Additional light snacks, fruits, and raw vegetables can be distributed to the subjects without restrictions at any time during confinement as long as they comply with the dietician's standard diet. Consumption of water is allowed as desired. Consumption of quinine-containing drinks (e.g., tonic water) is not allowed. The same menu and meal schedule will be administered uniformly for all subjects in all study arms. Fasting state has to be observed for at least 10 hours prior to blood drawings for the safety laboratory on the Screening Visit, on Day -1 and Day 4.

## 6.7 Concomitant Medication

For the purpose of this study, no concomitant medication should be taken by the subjects. Any medication with an impact on the CYP2A6 metabolism (as prescription and over-the-counter products) as given below must be avoided as CYP2A6 is involved in the nicotine metabolism.

In this study the use of hormonal contraception containing oestrogens is NOT allowed. This also applies to hormone replacement therapy. Only hormonal contraception with products containing progesterone is allowed during this study. Subjects using oestrogens during the study will be withdrawn.

The following drugs and substances are considered as having an impact on CYP2A6 activity ([Lacy et al, 2007: Table 2](#)). Prior to database close, the concomitant medication will be assessed according to the potential impact on CYP2A6 activity and the potential impact on study results.

**Table 2. Examples of Drugs and Substances Considered Interacting with CYP2A6**

Drug name	Substance Class
Fluoroquinolones, including ciprofloxacin and ofloxacin, nafcillin, rifampicin	Antibiotic
Fluvoxamine, fluoxetine, paroxetine, bupropion, duloxetine, amitriptyline, imipramine, sertraline, mirtazapine, citalopram, thioridazine	Antidepressant
Haloperidol, perphenazine, chlorpromazine, propoxyphene, fluphenazine, clozapine, olanzapine	Neuroleptic
Phenobarbital, primidone, carbamazepine	Antiepileptic
Chlorquine, quinidine	Antirheumatic
Clotrimazole, terbinafine, fluconazole, ketoconazole, miconazole	Antimycotic
Erythromycin, ciprofloxacin, clarithromycin, norfloxacin	Antibiotic
Cimetidine, chlorpheniramine, diphenhydramine, ranitidine	H2-receptor antagonist
Amiodarone, verapamil, mibepradil, mexiletine, propafenone, propranolol, lidocaine	Antiarrhythmic
Losartan, amlodipine, nifedipine, losartan	Antihypertensive
Drospirenone, oestrogens	Hormonal contraceptives Agents for hormonal replacement therapy (oestrogens)
Fluvastatin	Cholesterol-lowering agent
Theophylline	Antispasmodic pulmonological agent/Bronchodilator agent
Omeprazole, Lansoprazole	Proton pump inhibitor
Interferon	Antiviral/Immunomodulating agent
Methoxsalen	Anti-psoriatic (substance class Furocoumarins)
Modafinil, Diclofenac, Rofecoxib	Analgesic
Insulin	Anti-diabetic
Sildenafil	Phosphodiesterase-Inhibitor (e.g., used for treatment of Erectile dysfunction)

Confidentiality Statement: Data and information contained in this document are considered to constitute trade secrets and confidential commercial information, and the legal protections provided to such trade secrets and confidential information are hereby claimed under the applicable provisions of applicable law. No part of this document may be publicly disclosed without the written consent of Philip Morris Products S.A.

Quinine	Crystalline alkaloid
St. John's Wort	Over-the-counter (herbal remedy) antidepressant
Psoralen	Anti-psoriatic (substance class Furocoumarins)
Pilocarpine	Cholinergic agonists (e.g., used for Glaucoma Therapy)

Data sources: [Lacy et al, 2007](#). This list is not exhaustive.

However, the Investigator is responsible for the medical care of the subjects during their participation in this study. Any decisions regarding the prescription of medication will be taken in the best interest of the subject.

If the use of a concomitant medication cannot be avoided for the subject's safety it has to be fully documented (for details, see [Section 7.4.6](#)). Concomitant medications should be followed up with the CRO Medical Monitor on an ongoing basis.

Concomitant medication will first be assessed at Screening Visit. To be eligible for the study any medication with impact on CYP2A6 metabolism must be discontinued at least 14 days prior to Admission to the clinic or for at least five half-lives (whichever is longer). They must not be used during the entire study until the time of discharge. It is at the discretion of the Investigator to assess if a termination of such medication at Screening is medically justified and safe for the subject.

## 7 STUDY PROCEDURES

Personnel performing study measurements or recording must have the appropriate training fully documented. Quality and control measures have to be in place. All study procedures are provided as an overview in the Schedule of Events ([Appendix 1](#)). In this Section, only the expected/planned time points for the various measurements are given. Considering that not all subjects can have a procedure at the same time point, adequate time windows will be given for each study procedure and each time point in [Section 9](#). Site personnel will adhere to the site's Standard Operating Procedures (SOPs) for all activities. Appropriate medical advice will be provided to the subject in case of any medical findings requiring health care.

### 7.1 Informed Consent

Each subject must give his/her informed consent prior to participating in the study. During the consent process, the Investigator or designee obtaining consent must inform each subject of the nature, risks and benefits of, and alternatives to study participation. In addition, each subject must review the Subject Information Sheet and ICF and must have sufficient time to read and understand and have adequate opportunity to ask questions. The ICF must be signed and dated prior to undertaking any study-specific procedures. A signed copy should be given to the subject.

### 7.2 Smoking Cessation Advice and Debriefing

Each subject will be given advice on the risks of smoking three times during the study: at the Screening Visit, at Admission (Day -1), and at Day of Discharge (Day 4). This will take the form of a brief interview according to current World Health Organization (WHO) recommendations ([Raw et al, 2002](#)). Details of the interview will be recorded in the Source Document File. Information on the risks of smoking will be given to the subjects on an individual basis during a face-to-face meeting between the subject and the Investigator or designee and may additionally be given in a group session.

In addition to the smoking cessation advice, a debriefing of subjects will be done at each smoking cessation advice session to address any intended or unintended beliefs participants have about the candidate MRTP. The goal of the debriefing would be to help ensure that subjects exit the study with an accurate understanding of product risks, including an understanding that the candidate MRTP has not been demonstrated to be less harmful.

### 7.3 Support during Smoking Abstinence/Periods of Reduced Smoking

All subjects will be closely monitored by the site staff on D0, D1, D2, and D3. This includes monitoring of clinical tests e.g., vital signs, physical examination, and body weight. It also refers to close monitoring of the subject's behaviour, AEs, and his/her mood.

Confidentiality Statement: Data and information contained in this document are considered to constitute trade secrets and confidential commercial information, and the legal protections provided to such trade secrets and confidential information are hereby claimed under the applicable provisions of applicable law. No part of this document may be publicly disclosed without the written consent of Philip Morris Products S.A

## 7.4 Clinical Assessments

Any clinically relevant finding detected during the Screening Visit has to be documented as a concomitant disease. This also applies to clinically relevant findings in e.g., laboratory values, vital signs and ECGs, detected during the Screening Visit. Any untoward medical occurrence in a subject detected during the study which was not present at the Screening Visit must be documented as an AE. Worsening of a pre-existing condition from the Screening Visit onwards will also be documented as an AE. If a clinically relevant finding is detected during the Screening period, the Investigator needs to check if inclusion criterion no. 3 is still fulfilled.

### 7.4.1 Demographic Data

Demographic data (sex, date of birth/age, and race) will be recorded on the day of ICF signature.

### 7.4.2 Socio-Economic Status

At Day 2, subjects will be asked questions, which will allow the Sponsor to infer their socio-economic status (see [section 7.8.5](#)).

### 7.4.3 Identification of the Current Cigarette Brand

Identification of the current CC brand smoked by the subject will be done at the Screening Visit and at Day -1. For the Screening Visit, smokers will be asked to bring a packet of their current CC brand to the site. The site staff will document brand name and yields. At Day -1, subjects have to hand their CC supply for the confinement period to the site staff, who will take a photograph of the front and of the side of a cigarette pack with information of ISO nicotine, CO and tar supplied by the subject and will document brand name and yields. Photos will be considered as Source Documentation. A copy of the photos will be provided to the Sponsor electronically as Digital Versatile Disc (DVD) or Compact Disc (CD).

### 7.4.4 Smoking History and Willingness to Quit Smoking

Subjects will be questioned for their smoking history. At Screening and day of Admission, this will include questions to evaluate whether the subject was a smoker for at least the last three consecutive years, to determine the number of CC smoked during the previous 4 weeks, and to evaluate if the CCs smoked during the previous 4 weeks were non-menthol. Yields will later be ascertained, from the cigarette brands. At the Screening Visit only, the subject will also be asked if he/she is planning to quit smoking during the next 3 months. In addition, the subject will be asked if he/she has used nicotine-containing products other than commercially available CC (either tobacco-based products or NRT), electronic cigarettes or similar devices, within 4 weeks prior to assessment.

Furthermore, subjects will be asked if they are ready to abstain from smoking/accept reduced smoking frequency for up to 4 days. Only subjects prepared and able to comply with this requirement will be considered for participation in the study.

#### **7.4.5 Demonstration and Product Tests of THS 2.2 and NNS**

All subjects will have a demonstration of the THS 2.2 and the NNS products by the site staff at the Screening Visit. On Day -1, as the last procedure of the eligibility assessments, subjects will have a product test for the THS 2.2 (using up to three Tobacco Sticks) first and subsequently a product test of the NNS (spraying once in each nostril). In female subjects, the THS 2.2 and NNS product tests must only be done after pregnancy is excluded by a negative urine pregnancy test. Only subjects willing and ready to use the THS 2.2 and the NNS and be randomized to any of the study arms can be enrolled into the study.

#### **7.4.6 Medical History, Concomitant Disease, Previous and Ongoing Medications**

Relevant medical history and any concomitant disease will be documented at the Screening Visit. Medical history is defined as any condition that started prior to and ended prior to Screening. A concomitant disease is defined as any condition that started prior to the Screening Visit and is still ongoing at the Screening Visit.

Medication taken within 4 weeks prior to Screening Visit and any concomitant medication needs to be documented. Any medication which was started prior to the Screening Visit and is still being taken by the subject will be considered a concomitant medication. Medication initiated after Screening is also referred to as concomitant medication. This applies to both prescription and over-the-counter products.

Records should include the drug name (preferably both generic and trade name), route of administration, (e.g., oral, intravenous), total daily dose/unit (expressed in, for example, mg, mL, or IU), indication, the start and, if applicable, the stop date (day, month, and year). Therapy changes (including changes of regimen) during the study are to be documented. If a concomitant medication is still being taken by the subject at the end of the study, this will be recorded on the eCRF.

#### **7.4.7 Physical Examination**

A physical examination will be conducted at the Screening Visit, at Admission (Day -1) and at the Day of Discharge (Day 4).

#### **7.4.8 Body Height and Weight**

Body weight will be recorded at the Screening Visit, at Admission (Day -1) and at the Day of Discharge (Day 4). Body height will be measured at the Screening Visit, only. The BMI will

Confidentiality Statement: Data and information contained in this document are considered to constitute trade secrets and confidential commercial information, and the legal protections provided to such trade secrets and confidential information are hereby claimed under the applicable provisions of applicable law. No part of this document may be publicly disclosed without the written consent of Philip Morris Products S.A.

be calculated from the body weight and height using the following formula, rounded to one decimal place:

#### 7.4.9 **Vital Signs**

Systolic and diastolic blood pressure, pulse rate, and respiratory rate will be measured at the Screening Visit, at Admission, and at every day in confinement. All parameters will be recorded in supine position after the subject has rested for at least 5 minutes.

For every measurement it has to be documented if the subject has smoked within 15 minutes prior to the measurement.

#### 7.4.10 **Other Clinical Assessments**

##### 7.4.10.1 **Spirometry**

Spirometry with and without a short-acting bronchodilator will be done at the Screening Visit to evaluate inclusion/exclusion criteria (the post-bronchodilator results). At screening, spirometry without bronchodilator will be done first, and then, spirometry with bronchodilator. Furthermore, spirometry without a bronchodilator will be performed on Day-1 as well as on Day 4.

Spirometry will follow the 2005 testing and quality recommendations by the American Thoracic Society/European Respiratory Society Joint Task Force on the standardization of spirometry along with the electronic data submission and documentation processes ([American Thoracic Society \(ATS\), 2005](#)). Spirometry predicted values will be standardized to the National Health and Nutrition Examination Survey III predicted set ([Hu and Cassano \(NHANES III\), 2000](#)).

All personnel performing lung function testing should have the appropriate training and quality control measures should be put into place and be properly documented and filed at the pulmonary function laboratory (including the records of the calibration, if applicable). The FEV1 and FVC will be recorded.

The subject will be submitted to a spirometry with maximum voluntary ventilation measurement.

For spirometry, assessed parameters will include:

- FEV1.
- FVC.

**Confidentiality Statement:** Data and information contained in this document are considered to constitute trade secrets and confidential commercial information, and the legal protections provided to such trade secrets and confidential information are hereby claimed under the applicable provisions of applicable law. No part of this document may be publicly disclosed without the written consent of Philip Morris Products S.A.

- FEV1/FVC.

#### 7.4.10.2 Electrocardiogram

An ECG will be recorded at Screening and on the following study days: Day 1 and Day 3. The ECG testing will be performed as per the site local practice. A standard 12-lead ECG will be recorded after the subject has rested for at least 10 minutes in supine position.

The following parameters will be documented: heart rate, PR interval, QRS interval, QT interval and QTc interval, corrected by the ECG device according to Bazett's formula. Every ECG has to be assessed as normal, abnormal – clinically not relevant, or abnormal – clinically relevant. A diagnosis has to be provided in the eCRF for all ECGs assessed as abnormal – clinically relevant. ECG print-outs will be interpreted by a qualified physician. Any print-outs of ECGs on thermo-sensitive paper must be photocopied, initialled, dated, and stapled together for inclusion in the Source Data File.

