#### 12.1.2 Definitions for Statistical Data Analysis

Unless otherwise stated, for the purposes of statistical analyses, baseline is defined as the last available time point prior to  $T_0$  on Day 1, from 6:00 AM to 9:00 AM.

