#### 12.6.5 Safety Endpoints

In general, all safety data will be listed and tabulated on the safety population by sequence, using the approach described in [Section 12.1.3](#). Safety variables collected during exposure periods will also be reported by product exposure.

AEdatas will serve as the primary assessment of safety. Other safety variables monitored in this study include: respiratory symptoms (cough assessment VAS and Likert scales); vital signs (systolic and diastolic blood pressure, pulse rate, respiratory rate); spirometry; ECG data; clinical chemistry, haematology, and urine analysis safety panel; physical examination; and concomitant medication.

The number and percentage of subjects with AEs and SAEs will be tabulated by system organ class and preferred term. Summaries will also be presented for AEs leading to withdrawal, AEs leading to Death, AEs by relatedness to product exposure, AEs by severity, and laboratory AEs. Tabulations will be performed for both the number of subjects experiencing an event and the number of events. The number and percentage of device events and of subjects with device events will be tabulated by sequence.

Confidentiality Statement: Data and information contained in this document are considered to constitute trade secrets and confidential commercial information, and the legal protections provided to such trade secrets and confidential information are hereby claimed under the applicable provisions of applicable law. No part of this document may be publicly disclosed without the written consent of Philip Morris Products SA.

The number and percentage of subjects with clinical findings will be tabulated by sequence for laboratory parameters. Shift tables showing change from baseline of clinical findings will be provided for ECGs, physical examinations, and laboratory parameters (both shifts in normal ranges and toxicity grades). Descriptive statistics will be summarized by visit and change from baseline for laboratory parameters, ECG, respiratory symptoms, and vital signs.

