**Undesirable effects**

Some symptoms may be related to nicotine withdrawal associated with stopping smoking. These can include; irritability/aggression, dysphoria/depressed mood, anxiety, restlessness, poor concentration, increased appetite/weight gain, urges to smoke (cravings), night-time awakenings/sleep disturbance and decreased heart rate. Increased frequency of aphthous ulcer may occur after abstinence from smoking. The causality is unclear.

Nicorette Nasal Spray may cause adverse reactions similar to those associated with nicotine given by other means, including smoking, and these are mainly dose-dependent. At recommended doses Nicorette Nasal Spray has not been found to cause any serious adverse effects. Excessive use of Nicorette Nasal Spray by those who have not been in the habit of inhaling tobacco smoke could possibly lead to nausea, faintness or headaches.

During the first 2 days of treatment, nasal irritation as sneezing, running nose, watering eyes, cough was reported by nearly all (94%) of the patients. Both the frequency and severity declined with continued use. Reported adverse events associated with Nicorette Nasal Spray include:

Body System	Incidence*	Reported adverse event
Nervous system disorders:	Common	Dizziness, headache
Cardiac disorders:	Uncommon:	Palpitations
	Very rare:	Reversible atrial fibrillation
Respiratory, thoracic and mediastinal disorders:	Common:	Coughing
Gastrointestinal disorders:	Common:	Gastrointestinal discomfort, nausea, vomiting
General disorders and administration site disorders:	Very common:	Epistaxis, running nose, sneezing, watering eyes.

\* Very common (>1/10); common (>1/100, <1/10); uncommon (>1/1 000, <1/100); rare (>1/10 000, <1/1 000); very rare (<1/10 000), including isolated reports.”

Confidentiality Statement: Data and information contained in this document are considered to constitute trade secrets and confidential commercial information, and the legal protections provided to such trade secrets and confidential information are hereby claimed under the applicable provisions of applicable law. No part of this document may be publicly disclosed without the written consent of Philip Morris Products SA.

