## 6.2 Use of Investigational and Reference Point Products

Subjects will never be requested or forced to smoke and will be free to stop smoking at any time during the study. Subjects caught using any nicotine/tobacco product which is different from the assigned product will be withdrawn from the study. During the screening period, subjects will be allowed to smoke according to their smoking habits except during the procedures of the screening visit 9.1 at the discretion of the site.

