### 6.2.2 Investigational Period (Day 0 to Day 3)

During the first washout, each subject will maintain nicotine abstinence from Day -1 at 11:00 PM to the time of single use of his/her allocated product at Day 1. At Day 1, after the single use of the product, subjects will maintain nicotine abstinence for the rest of the day. During the second washout on Day 2, subjects will maintain nicotine abstinence until the time of single use of subject's allocated product at Day 3. Subjects will not be allowed to smoke or use any other nicotine/tobacco-containing products other than the products they are allocated to.

Time point of first product use during study day ( $T_0$ ) will be defined as start of the single product use at the single use days. The start of product use for THS 2.2 is defined as the time of the first puff. The start time for CC corresponds to the lighting of the CC, and the start time of the product is the time of the spray in the first nostril. The 30 seconds it takes to pre-heat the Holder will not be taken into account. **The subject must not take a puff of the Tobacco Stick during the pre-heating time.**

The start of the first product use can be different for each subject both days of product use; however, it must be in the window of 6:00 am to 9:00 am.

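### Bazett is the only QT correction named, while ECG change from baseline compares two different nicotine states; any heart-rate difference between them would shift the QTc change

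*Protocol*

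**What the plan says.** Section 7.4.10.2 lists the ECG parameters to be documented as "heart rate, PR interval, QRS interval, QT interval and QTc interval", the last of them "corrected by the ECG device according to Bazett's formula". It fixes the occasions: "An ECG will be recorded at Screening and on the following study days: Day 1 and Day 3". Table 8 places the ECG on Days 1 and 3 at 10:00–11:30 AM, and product use at 6:00–9:00 AM.

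Under section 12.1.2, unless otherwise stated, "baseline is defined as the last available time point prior to" T0 on Day 1. Section 12.6.5 plans descriptive statistics by visit and change from baseline for ECG, and adds: "Shift tables showing change from baseline of clinical findings will be provided for ECGs, physical examinations, and laboratory parameters". It plans no test on ECG data.

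On smoking state, section 6.2 says that during the screening period "subjects will be allowed to smoke according to their smoking habits", except during the visit procedures at the site's discretion. Section 6.2.2 says that "each subject will maintain nicotine abstinence from Day -1 at 11:00 PM" until the single product use on Day 1, and again from that use until the one on Day 3. Appendix 4, which reproduces the nasal-spray label, includes "night-time awakenings/sleep disturbance and decreased heart rate" among symptoms that may be related to nicotine withdrawal.

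The supplied protocol text holds two versions. Section 7.4.10.2 has the same wording in both. Table 8, section 12 and Appendix 4 appear only in the earlier one, because the text of the later one ends before them.

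**The concern.** No ECG is scheduled between Screening and T0 on Day 1, so the Screening ECG is the only one that can serve as baseline. It is taken up to four weeks before admission in people who smoke at least 10 cigarettes a day, and the time since the last cigarette is not controlled. Section 7.4.9 asks for smoking in the preceding 15 minutes to be documented for vital signs; section 7.4.10.2 has no such request for ECGs. The study-day ECGs are taken in a different nicotine state.

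A QT correction has to take heart rate out of such a comparison. Bazett divides QT by the square root of RR. If QT in these subjects follows a smaller power of RR, QTcB still moves with heart rate when repolarisation has not changed. The tabulated QTc change from Screening would then mix a rate artefact with any real effect, and a reader could not tell them apart from the QTc column alone.

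**Working it through.** **Timing, from sections 6.2.2 and 9.3.2**

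- 11:00 PM on Day -1 to T0 on Day 1 (6:00–9:00 AM): 1 + 24 + 6 = 31 h to 1 + 24 + 9 = 34 h.
- T0 on Day 1 to T0 on Day 3: 48 - 3 = 45 h to 48 + 3 = 51 h. Both intervals meet the protocol's stated minimum wash-out of 24 h.
- T0 to the ECG: 10:00 - 9:00 = 1 h to 11:30 - 6:00 = 5.5 h.
- Last *ad libitum* smoking to the Day 1 ECG: 35 to 36.5 h.
- Nicotine left from the single use at the ECG, with the protocol's half-life of about 2 h and decline counted from T0: 0.5^(1/2) = 71% to 0.5^(5.5/2) = 15%.

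**Rate artefact**

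The protocol states no QTc figure to reproduce. Three inputs are assumptions, because the documents give none of them: a true corrected QT of 400 ms at both visits, the relation QT = 400 × RR^b with RR = 60/HR in seconds, and the heart rates themselves. Then

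- QTcB = QT/RR^(1/2) = 400 × (60/HR)^(b - 1/2)
- QTcF = QT/RR^(1/3) = 400 × (60/HR)^(b - 1/3)

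With b = 1/3, QTcB is 419.6 ms at 80 bpm, 415.2 at 75, 410.4 at 70, 405.4 at 65 and 400.0 at 60. A fall from 75 to 65 bpm therefore gives 405.4 - 415.2 = -9.8 ms, and a rise from 65 to 75 bpm gives +9.8 ms.

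Change for a 10 bpm fall, by exponent:

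| b | Fall (bpm) | QTcB change (ms) | QTcF change (ms) |
|---|---|---|---|
| 1/3 | 80 to 70 | -9.2 | 0 |
| 1/3 | 70 to 60 | -10.4 | 0 |
| 0.37 | 80 to 70 | -7.1 | +1.9 |
| 0.37 | 70 to 60 | -8.1 | +2.3 |
| 0.42 | 80 to 70 | -4.3 | +4.5 |
| 0.42 | 70 to 60 | -5.0 | +5.3 |

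For b = 1/3 and a start of 70–80 bpm, a 5 bpm fall gives -4.5 to -5.0 ms in QTcB and a 15 bpm fall gives -14.3 to -16.2 ms. With no heart-rate change the artefact is 0 for any b.

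The zero for QTcF at b = 1/3 holds by construction. QTcF has the smaller artefact when b is below the midpoint of 1/3 and 1/2, which is 5/12 or about 0.417. At 0.42 the two artefacts are of similar size and opposite sign. For any b between 1/3 and 1/2, a change in heart rate moves QTcB and QTcF in opposite directions, so the pair brackets the true change.

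**Between products**

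Both products are measured on study days, so a shift from Screening that is common to both days drops out of the contrast within a subject. What remains depends on a product-specific difference in heart rate. At a reference of 65 bpm with b = 1/3, a difference of 3 bpm gives about 3 ms and one of 5 bpm about 5 ms.

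**The case against.** The strongest objection is that this belongs in the SAP. Section 7.4.10.2 says what the site records, and raw QT and heart rate are part of it. Nothing stops the SAP, which is not shown, from deriving another correction. It is true that nothing is foreclosed, and this is why the change is cheap. But the protocol does name a correction, and it is the only one in the plan.

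A second objection is that the contrast in nicotine state is blurred, and this stands. The study-day ECGs follow a nicotine product by 1 to 5.5 h, and at Screening smoking may be restricted during procedures. A reader might infer that the study ECGs reflect plain abstinence, so that heart rate must be lower and QTc falsely short. The documents do not support that. The label text in Appendix 4 says only that withdrawal symptoms can include a lower heart rate. It gives no figure and does not cover abstinence interrupted by a nicotine product. The net shift could be a fall, nothing or a rise.

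Third, the size depends on the assumed QT–RR relation. This also stands: moving b from 1/3 to 0.42 about halves the artefact.

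Fourth, heart rate is itself an ECG parameter and pulse rate is measured daily, so a rate shift would be visible elsewhere in the tables. The ECG shift tables concern clinical findings, not milliseconds of QTc. Both points are fair. They leave the numerical QTc change as the affected output, and the reader would have to make the rate adjustment unaided.

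**Conclusion.** The point holds as a limited one. The plan names one rate-dependent correction and applies change from baseline across two nicotine states. If heart rate differs between them and QT follows a power of RR below 1/2, the QTcB change carries an artefact: a fall in rate hides prolongation and a rise exaggerates it. For an assumed 10 bpm fall from 70–80 bpm the artefact is about -4 to -10 ms over exponents of 0.42 to 1/3. Neither the heart-rate shift nor the exponent is in the documents, so this is a conditional size and not an estimate of bias in this study.

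A reader might also infer that the THS 2.2 versus CC or NNS comparison of QTc is distorted to the same degree. It is not: the common part cancels, and only a product-specific heart-rate difference would remain. QTc is a descriptive safety variable, so no primary or tested result is affected. This is a cheap improvement. The reading relies on Table 8, section 12 and Appendix 4 of the earlier protocol version being unchanged in the later one.

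**What to change.** Derive QTcF = QT/RR^(1/3), with RR = 60/heart rate, from the QT and heart rate already recorded at each ECG. Base the descriptive QTc change-from-baseline summaries on QTcF, show QTcB alongside, and present heart-rate change in the same table. Showing both matters because QTcF is not exact either: if they disagree and heart rate has moved, the reader can see a rate artefact and its likely direction.

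The cost is one derived variable and one more table column. The ECG schedule, the device settings and the data collected stay as they are.
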